#### 4.1.5 Aqueous Humor Pharmacokinetic-Evaluable Population

The Aqueous Humor PK-Evaluable Population is the subset of patients in the PK-Evaluable Population with at least one optional aqueous-humor sample.

## 4.1.6 Safety Population

Safety data will be summarized on the Safety Population comprising all patients who receive the study treatment, with patients grouped according to treatment actually received.

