#### Table 2 Dosing Guidelines during Run-in Period and at Screening Visit

Anti-VEGF = anti-vascular endothelial growth factor.

a Randomization and the Day 1 visits should be completed within 21–28 days (inclusive) after last ranibizumab dose in the study eye.

All patients will return for a randomization visit and the Day 1 visit within 21–28 days (inclusive) after their last ranibizumab dose.

Patients who are randomly allocated to the implant arm will have the implant (pre-filled with ranibizumab 100 mg/mL) surgically inserted on Day 1, which must occur 1–7 days (inclusive) after randomization (i.e., randomization and Day 1 visit assessments cannot be performed on the same day) and no later than 28 days from the last intravitreal ranibizumab 0.5 mg injection. If the implant insertion surgery (Day 1) cannot be completed within the visit window after randomization, the randomization visit assessments may be repeated and an additional intravitreal ranibizumab 0.5 mg injection may be required after discussion with the Sponsor. After Day 1, patients in the implant arm will have scheduled safety visit assessments on Days 2 and 7 ( $\pm$ 2 days) and will receive implant refill-exchanges with ranibizumab 100 mg/mL Q24W at Week 24 ( $\pm$ 7 days), Week 48 ( $\pm$ 7 days), and Week 72 ( $\pm$ 7 days).

Patients who are randomly allocated to the intravitreal arm will receive intravitreal ranibizumab 0.5 mg injections starting on Day 1, which is to be administered at the conclusion of the randomization visit (i.e., randomization and Day 1 visit assessments are performed on the same day). Patients will receive ranibizumab 0.5 mg, injected intravitreally Q4W ( $\pm$ 7 days) from Day 1 until Week 92.

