#### 3.2 INTERNAL SAFETY MONITORING

A safety team will closely monitor patient safety throughout the study to ensure early identification and corrective action of procedure- and operator-associated adverse events for individual patients.

Unmasked safety data will be reviewed on a routine basis by the Sponsor's safety team in order to expeditiously identify and manage risks. The efficacy data will not be reviewed during internal safety monitoring.

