# 5.3.1 Adverse Event Reporting Period

Investigators will seek information on adverse events at each patient contact. All adverse events, whether reported by the patient or noted by study personnel, will be recorded in the patient's medical record and on the Adverse Event eCRF.

After informed consent has been obtained but prior to initiation of study treatment (Day 1), only serious adverse events caused by a protocol-mandated intervention (e.g., discontinuation of medications or intravitreal ranibizumab administered at screening or during run-in period) should be reported (see Section 5.4.2 for instructions for reporting serious adverse events).

After initiation of study treatment, all adverse events, regardless of relationship to study drug, implant, or ancillary devices, or study procedures, will be reported until the patient's final study visit. For patients who terminate study treatment and discontinue from the study prematurely, all adverse events will be reported up to the early termination visit. For patients who discontinue study treatment early but continue to participate in the study, adverse events will be reported until their last or final study visit.

Instructions for reporting adverse events that occur after the adverse event reporting period are provided in Section 5.6.

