#### 5.3.4 Assessment of Causality of Adverse Events

Investigators should use their knowledge of the patient, the circumstances surrounding the event, and an evaluation of any potential alternative causes to determine causality of an adverse event. Investigators will assess any relationship between the adverse event

**Port Delivery System with Ranibizumab—F. Hoffmann-La Roche Ltd.** 90/Protocol GR40548, Version 5

and each component separately, indicating "yes" or "no" as applicable on Adverse Event eCRF.

**Patients in the Implant Arm**: The investigator will assess whether there is a potential association with each of the following "components" of the study intervention:

- Implant, insertion tool, or implant procedure
- Refill-exchange or refill needle
- Explant or explant tool
- Ranibizumab (study drug)

**Patients in the Intravitreal Arm**: The investigator will assess whether there is a potential association with each of the following "components" of the study intervention:

- The intravitreal injection procedure
- Ranibizumab (study drug)

The following guidance should be taken into consideration when assessing causality:

- Temporal relationship of event onset to the initiation of study drug, implant and its insertion, refill-exchange, or explantation procedures or due to other PDS components (see Table 11) or due to intravitreal injection procedure.
- Course of the event, considering especially the effects of dose reduction, discontinuation of study drug, or reintroduction of study drug (as applicable)
- Known association of the event with study drug, implant or other PDS components/procedures, or with similar treatments
- Known association of the event with the disease under study
- Presence of risk factors in the patient or use of concomitant medications known to increase the occurrence of the event
- Presence of non-treatment-related factors that are known to be associated with the occurrence of the event

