#### 6.5 SAFETY ANALYSES

Safety data will be summarized on the safety population comprising all patients who receive study treatment, with patients grouped according to treatment actually received (patients who receive PDS implant will be included in the implant arm).

Safety will be assessed through descriptive summaries of adverse events, ocular assessments, and ADAs to ranibizumab. Clinically significant laboratory abnormalities and clinically significant vital sign abnormalities will be reported as adverse events and evaluated as part of the adverse event assessments.

At the time of the primary analysis, safety summaries will be summarized based on the complete Week 40 data in the safety population. In addition, ongoing safety data (from first treatment up to a single specified clinical cutoff date) in the safety population will also be summarized. At the time of the final analysis, safety summaries will be produced based on cumulative data in the safety population.

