#### 4.2 ANALYSIS OF STUDY CONDUCT

Patient disposition (the number of patients randomized, treated, and completing each study period) will be tabulated by treatment actually received in Efficacy Population. Reasons for premature study treatment discontinuation and study discontinuation will be tabulated and a listing will be provided. Detailed, free text reasons are collected for discontinuations due to physician decision and 'other' reasons. This information will be included in the listing.

Eligibility criteria deviation and other major protocol deviations will be tabulated and a listing will be provided.

Exposure to study treatment (number of study treatments [PDS refill-exchanges, intravitreal ranibizumab injection, supplemental intravitreal ranibizumab injection] and duration of treatment) will be summarized by treatment group for the study eye in the Safety Population.

Duration of treatment is the time from first study treatment (implant or intravitreal ranibizumab injection) to the earlier of:

- The date of treatment discontinuation or date of study completion
- The analysis cutoff date

Pre-treatment and concomitant systemic medications, ocular medications for the fellow eye and, ocular medications for the study eye will be summarized separately by treatment group. Measures were implemented to mitigate the risk to data integrity posed by coronavirus disease 2019 (COVID-19). The impact of COVID-19 will be assessed in the COVID-19 Clinical Study Report (CSR) Annex in terms of the following criteria:

- Early study treatment discontinuation due to COVID-19
- Missed treatments due to COVID-19 or related precautions
- Use of prohibited therapy due to COVID-19
- Missing BCVA or BCVA not performed per protocol due to COVID-19 or related precautions

- Major protocol deviations associated with COVID-19 directly or indirectly
- Missed visits reported as due to COVID-19 or related precautions
- Early study discontinuation due to COVID-19
- Death due to COVID-19
- Confirmed or suspected cases of COVID-19 and adverse events (AEs) associated with COVID-19

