#### 4.3 ANALYSIS OF TREATMENT GROUP COMPARABILITY

Demographic and baseline characteristics, such as age, sex, race, baseline disease characteristics (such as baseline center point thickness [CPT], and baseline BCVA), and number of prior anti-VEGF injections, will be summarized in the Efficacy Population by treatment group using descriptive statistics.

Baseline is defined as the last available measurement prior to first study treatment (PDS implant or post-randomization intravitreal injection).

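### On the more natural reading, a patient whose implant insertion is started, abandoned and never completed is left out of the implant arm's safety tables

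*SAP*

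**What the plan says.** SAP 4.1.6 defines the population for all safety summaries: "Safety data will be summarized on the Safety Population comprising all patients who receive the study treatment". Patients are then grouped by the treatment they actually received. Protocol 6.5 has the same rule and adds that "patients who receive PDS implant will be included in the implant arm".

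The SAP indicates in two places what it means by first study treatment. Section 4.2 says "Duration of treatment is the time from first study treatment (implant or intravitreal ranibizumab injection", and section 4.3 sets baseline as the last measurement "prior to first study treatment (PDS implant or post-randomization intravitreal injection". In SAP 4.7.1 and Protocol 6.5.1, the treatment-emergent period starts at surgical insertion of the implant or at the first intravitreal injection (post-randomization, in the SAP's wording).

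The protocol also treats the operation as part of what is being tested. In the implant arm, Protocol 5.3.4 has the investigator judge causality separately for several components, of which the first is "Implant, insertion tool, or implant procedure". No section says how to classify a patient in whom insertion was started but not completed.

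**The concern.** Harm from the operation can arise before the device is in place. The implant goes in through an incision in the sclera and pars plana (Protocol Appendix 16), and suspicious peripheral retina is to be treated before insertion (Protocol 5.1.3.5). A surgeon may have to stop after either step. If membership of the implant arm depends on receiving the implant, a complication in such a patient is missing from both the numerator and the denominator of the implant arm's adverse-event rates. The control arm has no surgery, so only the implant arm can lose patients in this way.

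The other planned outputs do not clearly bring the patient back. SAP 4.2 tabulates disposition in the Efficacy Population, which also requires receipt of study treatment. The listing of deaths and the tables of protocol deviations do not report adverse events of an abandoned operation. At stake is how completely the tables describe the risk of undertaking the procedure. No efficacy result, power figure or formal test is affected.

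**Working it through.** **What the text implies.** Entry to the Safety Population requires receiving study treatment (SAP 4.1.6). For the implant arm, the SAP names that treatment as the implant (4.2, 4.3), and Protocol 6.5 groups by receipt of the implant. A patient with an abandoned insertion and no later implant has not received it, and so is outside the implant arm's tables. A patient who is implanted at a later attempt is back in the implant arm. The gap is therefore limited to those never implanted.

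**Inputs.** The plan gives no figure on this point, so there is none to reproduce. Total enrolled is 418 and allocation is 3:2 (SAP 2.2). Assumption: enrolment split exactly in that ratio.

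- Implant arm: 418 × 3/5 = 250.8, about 251.
- Intravitreal arm: 418 × 2/5 = 167.2, about 167.

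These are enrolled counts, not treated counts. The number of abandoned insertions and all event counts below are assumptions.

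**One omitted patient who had the event.** With x true cases, the rate goes from x/251 to (x − 1)/250.

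| x | All counted | One omitted | Change (points) |
|---|---|---|---|
| 1 | 0.398% | 0.000% | −0.40 |
| 3 | 1.195% | 0.800% | −0.40 |
| 5 | 1.992% | 1.600% | −0.39 |
| 10 | 3.984% | 3.600% | −0.38 |

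**One omitted patient without the event.** The rate goes from x/251 to x/250. At x = 5 it rises from 1.992% to 2.000%, or 0.008 points; at x = 10 it rises by 0.016. This small effect goes against the implant.

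**More than one abandoned insertion.** Take 4 events among implanted patients and k abandoned insertions, each with an event (an upper case). The rate is (4 + k)/251 if they are counted and 4/(251 − k) if they are omitted.

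| k | Counted | Omitted | Shortfall (points) |
|---|---|---|---|
| 0 | 4/251 = 1.59% | 4/251 = 1.59% | 0 |
| 1 | 5/251 = 1.99% | 4/250 = 1.60% | 0.39 |
| 2 | 6/251 = 2.39% | 4/249 = 1.61% | 0.78 |
| 3 | 7/251 = 2.79% | 4/248 = 1.61% | 1.18 |
| 5 | 9/251 = 3.59% | 4/246 = 1.63% | 1.96 |

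**Between-arm difference, with 5 true implant-arm cases and 1 intravitreal case.**

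- All counted: 5/251 − 1/167 = 1.992 − 0.599 = 1.39 points.
- One affected patient omitted: 4/250 − 1/167 = 1.600 − 0.599 = 1.00 points.
- Same patient moved to the intravitreal arm, event at surgery: the event precedes that patient's first injection, so it is not treatment-emergent in that arm. The patient adds 1 to the denominator only: 4/250 − 1/168 = 1.600 − 0.595 = 1.00 points, the same as omission to two decimals.

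**The case against.** The strongest case is that the text can be read the other way. Protocol 3.1 runs visits from Day 1, which it equates with first study treatment, and for the implant arm Day 1 is the surgery visit. SAP 4.7.1 sets its onset windows from first dose or implant surgery. Together with Protocol 5.3.4, these would let a patient operated on at Day 1 count as having started study treatment. This stands as a reasonable alternative. It does not displace the requirement to receive treatment in SAP 4.1.6 or the naming of the implant in 4.2 and 4.3, and the existence of two readings is a reason to state the rule.

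It can also be said that little depends on it: the set may be empty and safety is assessed mainly by descriptive summaries. That is fair, and it limits the severity.

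Two stronger inferences are tempting, and the documents do not support them.

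A reader might infer that harm from a failed insertion is counted against the comparator. When surgery misses its window, Protocol 3.1 does say that "an additional intravitreal ranibizumab 0.5 mg injection may be required after discussion with the Sponsor", and 4.6.1 supplies ranibizumab to patients who discontinue from the implant arm. But Protocol 4.3.2.2 lists injections as study treatment only for the intravitreal arm, and separately from injections given when surgery is delayed or after discontinuation. The provision in 3.1 concerns rescheduling, after which an implant may follow. Regrouping is thus only a possible secondary case. The gap would shrink to 4/250 − 2/168 = 1.600 − 1.190 = 0.41 points only if the patient were never implanted, were injected after randomization, had that injection classed as study treatment, and had an event with onset on or after it.

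A reader might also infer that the harm would go unseen. Before study treatment starts, Protocol 5.3.1 requires reporting of "only serious adverse events caused by a protocol-mandated intervention". Protocol 3.2 has the safety team monitor for "early identification and corrective action of procedure- and operator-associated adverse events for individual patients", and the iDMC reviews individual patients (3.3). Detection is covered; placing the event in the implant arm's rate is not.

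**Conclusion.** The point holds as a minor one. On the more natural reading of SAP 4.1.6 with 4.2, 4.3 and Protocol 6.5, a patient with a started, abandoned and never completed insertion is left out of the implant arm's safety tables. The main effect is omission, worth about 0.4 percentage points of the implant-arm rate for each omitted patient who had the event, and a negligible rise for each who did not. Regrouping, if it happened, would ordinarily give the same between-arm difference as omission, about 1.00 against 1.39 points in the example.

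The sizes rest on an exact 3:2 split of 418 enrolled patients and on illustrative event counts. The documents describe no abandoned insertion, so the true effect may be nil. They do not show that the implant arm's safety results are wrong, or that events have been assigned to the comparator.

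**What to change.** **SAP 4.1.6:** *The Safety Population includes all patients who receive study treatment or in whom implant insertion surgery is started; patients with started insertion surgery are included in the implant arm.*

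**SAP 4.7.1:** *For the implant arm, the treatment-emergent period starts at the start of the first insertion procedure. The 37-day postoperative window runs from the successful insertion, or from the attempted procedure if the patient is never implanted; events between a failed attempt and a later insertion are counted in the postoperative period. Device-dislocation and refill-exchange events use the implanted denominator.*

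**SAP 4.1.3, 4.1.7, 4.2 and 4.7.6:** keep the PK, biomarker, exposure and anti-drug-antibody summaries limited to patients who received study treatment. The PK and biomarker sets and antibody incidence at entry are built on the Safety Population and would otherwise change with it.

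**Final CSR:** state the number of uncompleted insertions (including zero), list their adverse events, and footnote any denominator that differs from the Primary and Update CSRs, which were complete when SAP version 3 was written.

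**Cost.** A few SAP sentences and one listing. SAP section 1 gives the SAP precedence over the protocol's analysis plan, so no protocol amendment is needed. The implant-arm rate may become slightly less favourable, and denominators may differ slightly from the earlier reports. Data should be available: footnote h to Protocol Appendix 1, Table 1 has adverse events recorded from Day 1, so non-serious events of a Day 1 attempt should be on file.

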# 4.1.7 Biomarker Analysis Population

The Biomarker Analysis Population will consist of patients who are in the Safety Population and have sufficient data to enable assessment of potential changes in biomarkers in response to treatment during the conduct of this study. The analysis will group patients according to treatment actually received.

#### 4.2 ANALYSIS OF STUDY CONDUCT

Patient disposition (the number of patients randomized, treated, and completing each study period) will be tabulated by treatment actually received in Efficacy Population. Reasons for premature study treatment discontinuation and study discontinuation will be tabulated and a listing will be provided. Detailed, free text reasons are collected for discontinuations due to physician decision and 'other' reasons. This information will be included in the listing.

Eligibility criteria deviation and other major protocol deviations will be tabulated and a listing will be provided.

Exposure to study treatment (number of study treatments [PDS refill-exchanges, intravitreal ranibizumab injection, supplemental intravitreal ranibizumab injection] and duration of treatment) will be summarized by treatment group for the study eye in the Safety Population.

Duration of treatment is the time from first study treatment (implant or intravitreal ranibizumab injection) to the earlier of:

- The date of treatment discontinuation or date of study completion
- The analysis cutoff date

Pre-treatment and concomitant systemic medications, ocular medications for the fellow eye and, ocular medications for the study eye will be summarized separately by treatment group. Measures were implemented to mitigate the risk to data integrity posed by coronavirus disease 2019 (COVID-19). The impact of COVID-19 will be assessed in the COVID-19 Clinical Study Report (CSR) Annex in terms of the following criteria:

- Early study treatment discontinuation due to COVID-19
- Missed treatments due to COVID-19 or related precautions
- Use of prohibited therapy due to COVID-19
- Missing BCVA or BCVA not performed per protocol due to COVID-19 or related precautions

- Major protocol deviations associated with COVID-19 directly or indirectly
- Missed visits reported as due to COVID-19 or related precautions
- Early study discontinuation due to COVID-19
- Death due to COVID-19
- Confirmed or suspected cases of COVID-19 and adverse events (AEs) associated with COVID-19

Additional details on the analysis to address the impact of COVID-19 are provided in Section 4.4. The impact of COVID-19 on safety analysis is expected to be low since physicians will retrospectively collect safety events following missed visits; hence, the safety analysis plan is not amended except that additional summaries/listings will be provided for confirmed or suspected COVID-19 infection and AEs associated with COVID-19, as described in Section 4.7.2.

#### 4.3 ANALYSIS OF TREATMENT GROUP COMPARABILITY

Demographic and baseline characteristics, such as age, sex, race, baseline disease characteristics (such as baseline center point thickness [CPT], and baseline BCVA), and number of prior anti-VEGF injections, will be summarized in the Efficacy Population by treatment group using descriptive statistics.

Baseline is defined as the last available measurement prior to first study treatment (PDS implant or post-randomization intravitreal injection).

#### 4.4 EFFICACY ANALYSIS

The efficacy analyses will be based on the Efficacy Population.

Patients in the PDS 100 mg/mL arm can receive intravitreal ranibizumab injection as supplemental treatment if they meet the criteria described in Section 2.

Unless otherwise noted, analyses of efficacy outcome measures will be stratified by baseline BCVA (<74 letters vs.≥74 letters). The stratification factor as recorded in IxRS will be used. The estimates and confidence intervals (CIs) will be provided for the mean (for continuous variables) or proportion (for binary variables) for each treatment group and the difference in means or proportions between two treatment groups. All CIs will be two-sided and at the 95.03% level (see Section 3.3).

# 4.4.1 Primary Efficacy Endpoint

The primary efficacy endpoint is the change in BCVA score from baseline averaged over Weeks 36 and 40 with BCVA assessed using the ETDRS chart at a starting distance of 4 meters. The primary estimand is defined as follows:

- Population: Adult patients with nAMD diagnosed within 9 months and receiving at least 4 anti-VEGF intravitreal injections (with the last injection being ranibizumab), responsive to prior anti-VEGF treatment
- Variable: Change in BCVA score from baseline averaged over Weeks 36 and 40
- Intercurrent events: Regardless whether or not a patient has the following intercurrent event prior to Week 40:
  - -Receives more than 1 supplemental treatment
  - -Receives any prohibited systemic treatment or prohibited therapy in the Study eye (Section 4.4.2 of the Protocol)
  - -Discontinues study treatment due to AEs
  - Discontinues study treatment due to lack of efficacy as per investigator's clinical judgment
- Population-level summary: Difference in adjusted mean between PDS 100 mg/mL and intravitreal groups

Of note, lack of efficacy includes investigators choices for reason for discontinuation from treatment of lack of efficacy, progressive disease, disease relapse, and symptomatic deterioration.

The primary objectives are to determine the NI and equivalence between the two treatment groups, as measured by the primary efficacy endpoint with a NI margin of 4.5 letters and equivalence margins of  $\pm 4.5$  letters. To control the overall type I error, a fixed sequence testing procedure (Westfall and Krishen 2001) will be used. If the PDS 100 mg/mL arm is shown to be non-inferior to the intravitreal arm at the one-sided 0.02485 level, then the equivalence test will be conducted using two one-sided 0.02485 tests.

The primary analysis will be performed using the mixed-effect model with repeated measures (MMRM) based on all available data up to Week 40. All observed measurements will be included in the analysis regardless whether or not a patient has an intercurrent event. Missing data will be implicitly imputed by the MMRM model, assuming a missing at random mechanism.

The dependent variable in the MMRM model is the change from baseline in BCVA score at post-baseline visits, up to 40 weeks, and the independent variables are the treatment group, time, treatment-by-time interaction, baseline BCVA score (continuous), and the randomization stratification factor of baseline BCVA (<74 letters vs.≥74 letters) as fixed

effects. The MMRM model will assume an unstructured covariance structure. If there are convergence problems with the model, then a compound symmetry covariance or a first order autoregressive order (AR [1]) covariance structure will be used. Comparisons between the two treatment groups will be made using a composite contrast over Weeks 36 and 40.

For the primary efficacy endpoint, if a lower bound of a two-sided 95.03% CI for the difference of two treatments is greater than -4.5 letters (the NI margin), then treatment via PDS is considered non-inferior to monthly intravitreal ranibizumab treatment. If the two-sided 95.03% CI is within -4.5L and +4.5L, then the two treatment regimens are considered clinically equivalent.

As a sensitivity analysis the per-protocol analysis will follow the same methods as the primary analysis except the Per-Protocol Population will be used.

